3.3 Trial Endpoints

3.3.1 Primary Endpoint

The primary aim of the trial is to demonstrate that AMT-061 will provide a minimal therapeutic response of \geq 5% factor IX activity using a dose of 2 x 10¹³ gc/kg. This is the proposed dose to be used in a further pivotal Phase 3 trial. The primary efficacy parameter is factor IX activity level at six weeks after dosing (at Week 6 post AMT-061 dose).

3.3.2 Secondary Endpoints

Secondary efficacy endpoints:

- Endogenous factor IX activity at Week 6 and Week 52 post AMT-061 dosing
- Remaining free of previous continuous prophylaxis during 52 weeks following AMT-061 dosing
- Total usage of factor IX replacement therapy until 52 weeks following AMT-061 dosing, excluding ad hoc prophylaxis for invasive procedures
- Annualized bleeding rate after 52 weeks of AMT-061 dosing (including a further break down of the frequency and percentage of spontaneous, traumatic, and joint bleeding events)

CCI

Secondary safety endpoints

- AEs
- Hematology and serum chemistry parameters
- ALT/AST levels and corticosteroid use for ALT/AST elevations
- Parameters on antibody formation to AAV5 and human factor IX

AMT-061 (AAV5-hFIXco-Padua; etranacogene dezaparvovec) Protocol ID: CT-AMT-061-01

- AAV5 capsid-specific T cell response
- Inflammatory markers
- Vector DNA in semen and blood
- AFP

Safety endpoints are observed over the 52-week post-treatment follow-up phase and for an additional four years in the long-term follow-up phase. An additional endpoint in the long-term follow-up is abnormal findings on the abdominal ultrasound.

3.4 Sample Size

A minimum of three subjects will be enrolled in the trial (see also Section 9.11). To account for drop-outs additional subjects may be recruited.

3.5 Sites and Regions

It is planned to conduct this trial in approximately three sites in the United States (US) and the European Union (EU).

AMT-061 (AAV5-hFIXco-Padua; etranacogene dezaparvovec) Protocol ID: CT-AMT-061-01

4 TRIAL POPULATION

Subjects will be adult males with severe or moderately severe hemophilia B.

4.1 Inclusion Criteria

The subject cannot be enrolled in the trial before all of the following inclusion criteria (including test results) are met:

- 1. Male
- 2. Age ≥ 18 years
- 3. Subjects with congenital hemophilia B classified as one of the following:
 - a. Known severe factor IX deficiency (<1% of normal circulation factor IX) for which the subject is either on continuous routine factor IX prophylaxis* or using on-demand factor IX replacement therapy
 - b. Known moderately severe factor IX deficiency (1-2% of normal circulating factor IX, inclusive) and a severe bleeding phenotype as defined by at least one of the following:
 - i. On continuous routine factor IX prophylaxis* for a history of bleeding
 - ii. On demand factor IX replacement therapy with a history of frequent bleeding (4 or more bleeding episodes in the last 12 months) or chronic hemophilic arthropathy (pain, joint destruction, and loss of range of motion) in one or more joints
- 4. >20 previous exposure days of treatment with factor IX protein
- Acceptance to use a condom during sexual intercourse in the period from IMP administration until AAV5 has been cleared from semen, as evidenced by the central laboratory from negative analysis results for at least three consecutively collected semen samples (this criterion is applicable also for subjects who are surgically sterilized)
- 6. Able to provide informed consent following receipt of verbal and written information about the trial

* Continuous routine prophylaxis is defined as the intent of treating with an a priori defined frequency of infusions (e.g., twice weekly, once every two weeks, etc.) as documented in the medical records.

4.2 Exclusion Criteria

Subjects are excluded from the trial if any of the following exclusion criteria are met:

- 1. History of factor IX inhibitors
- 2. Positive factor IX inhibitor test at screening
- 3. Screening laboratory values:
 - a. ALT >2 times ULN
 - b. AST >2 times ULN

AMT-061 (AAV5-hFIXco-Padua; etranacogene dezaparvovec) Protocol ID: CT-AMT-061-01

- c. Total bilirubin >2 times ULN
- d. Alkaline phosphatase (ALP) >2 times ULN
- e. Creatinine >2 times ULN
- Positive HIV serological test at screening, not controlled with anti-viral therapy as shown by CD4+ counts ≤200/µL or by a viral load of >200 copies/mL
- 5. Active infection with Hepatitis B or C virus as reflected by hepatitis B surface antigen (HBsAg), hepatitis B extracellular antigen (HBeAg), hepatitis B virus deoxyribonucleic acid (HBV DNA) or hepatitis C virus RNA (HCV RNA) positivity, respectively, at screening
- 6. History of hepatitis B or C exposure, currently controlled by antiviral therapy
- 7. Known coagulation disorder other than hemophilia B
- 8. Thrombocytopenia, defined as a platelet count below $50 \times 10^9/L$, at screening
- 9. Known severe infection or any other significant concurrent, uncontrolled medical condition including, but not limited to, renal, hepatic, cardiovascular, hematological, gastrointestinal, endocrine, pulmonary, neurological, cerebral or psychiatric disease, alcoholism, drug dependency or any other psychological disorder evaluated by the Investigator to interfere with adherence to the protocol procedures or with the degree of tolerance to the IMP
- 10. Known significant medical condition that may significantly impact the intended transduction of the vector and/or expression and activity of the protein, such as disseminated intravascular coagulation, accelerated fibrinolysis, and profound liver fibrosis
- 11. Known history of an allergic reaction or anaphylaxis to factor IX products
- 12. Known uncontrolled allergic conditions or allergy/hypersensitivity to any component of the IMP excipients
- 13. Known medical condition that would require chronic administration of steroids
- 14. Previous gene therapy treatment
- 15. Receipt of an experimental agent within 60 days prior to screening
- 16. Current participation or anticipated participation within one year after IMP administration in this trial in any other interventional clinical trial involving drugs or devices

4.3 Reproductive Potential

Male subjects who participate in this trial accept to use a condom during sexual intercourse in the period from IMP administration until AAV5 has been cleared from semen, as evidenced by the central laboratory from negative analysis results for at least three consecutively collected semen samples (this criterion is applicable also for subjects who are surgically sterilized).

Subjects are being asked to inform their partner of their participation in this trial, as well as the importance of contraception use to limit the reproductive potential in the period from IMP administration until AAV5 has been cleared from the semen.

4.4 Restrictions

There is one restriction associated with participation in this trial, which is related to reproduction and described in Section 4.3.

4.5 Withdrawal of Subject from Therapy or Assessment

A subject may withdraw from the trial at any time, for any reason, without prejudice to their future medical care by his/her physician or at the institution. The Investigator or Sponsor may withdraw the subject at any time if it is not in the best interest of the subject to continue participation. Since this is a gene therapy trial in which the IMP is administered to human subjects as a one-time only dose, the Investigator should make all reasonable attempts to maintain the subject is withdrawn from the trial after IMP administration to allow long-term follow-up on safety. Where a subject is withdrawn from the trial at his own request or based on a decision of the Investigator, the safety follow-up should be maintained, conditional to the consent of the subject. The safety follow-up will include periodic review (approximately every 6 months) of medical records to gather information obtained during routine visits from the subject with his treating physician for the time until 5 years post IMP administration. Information on AEs, SAEs, concomitant medication use, and laboratory assessments will be collected as available. If a subject is to withdraw from the trial, the Investigator should make all reasonable attempts to have the subject sign the separate informed consent form (ICF) in order to maintain the long-term safety follow-up.

Subjects withdrawing from the trial will be requested to complete the same final evaluations (see Section 4.1) as subjects completing the trial according to the protocol, particularly safety evaluations in the subject's interest so that data can be recorded in the same way as for subjects who completed the trial. Comments (spontaneous or elicited) or complaints made by the subject must be recorded in the source documents. The reason for (if given) and date of withdrawal, must be recorded on the electronic case report form (eCRF) and source documents.

Subjects who withdraw prior to IMP administration or within the first six weeks after IMP administration will be replaced. Subjects who discontinue after six weeks post IMP administration will not be replaced.

4.5.1 Reasons for Discontinuation

The reasons for discontinuation from this gene therapy trial include:

- AE
- Withdrawal by principal Investigator
- Withdrawal by subject
- Lost to follow-up

4.5.2 Subjects 'Lost to Follow-up' Prior to Last Scheduled Visit

At least three documented attempts must be made to contact any subject lost to follow-up at any time point prior to the last scheduled contact (office visit or telephone contact). One of these documented attempts must include a written communication sent to the subject's last known address via courier or mail (with an acknowledgement of receipt request) asking that they return the e-diary device (if applicable) and return to the site for final safety evaluations.

5 TRIAL TREATMENT

5.1 Treatment(s) Administered

The IMP is identified as AAV5-hFIXco-Padua (hereafter referred as AMT-061; etranacogene dezaparvovec). AMT-061 is a recombinant adeno-associated viral vector of serotype 5 (AAV5) containing the Padua variant of a codon-optimized human factor IX cDNA under the control of a liver-specific promoter. The pharmaceutical form of AMT-061 is a solution for IV infusion.

Subjects will receive a single IV infusion of 2 x 10^{13} gc/kg AMT-061.

5.3 Dosing and Administration

AMT-061 will be administered at a dose of 2×10^{13} gc/kg as a one-time infusion in a peripheral vein. The subjects will be monitored for tolerance to the IMP and detection of immediate AEs for 24 hours (overnight stay) after dosing.

The dosing of the subjects must be separated by a minimum of 14 calendar days to allow for subject safety monitoring and to ensure appropriate action can be taken in case any acute reactions are observed.

Detailed instructions for IMP handling e.g., receipt, storage, preparation, administration, cleaning, destruction and the recording of these critical activities will be described in the IMP Handling Manual.

5.4 Randomization and Blinding

Not applicable, as this is an open-label trial with one treatment arm.

5.5 Labeling, Packaging, Storage, and Handling

All medication used in this trial will be prepared and labeled according to the rules of Good Manufacturing Practice, International Council for Harmonisation (ICH)-Good Clinical Practice (GCP) (E6[R2]) and local regulatory requirements. Further details on IMP labeling, packaging and handling, e.g., receipt, storage, preparation, administration, cleaning, destruction, documentation etc., will be described in the IMP Handling Manual.

5.6 Prior and Concomitant Medication/Therapy

5.6.1 **Prior Medication/Therapy**

Prior medication/therapy includes medication/therapy (including herbal treatments, vitamins, non-pharmacological treatment such as psychotherapy as appropriate) received within 30 days of and discontinued prior to the date of screening. Prior medication/therapy information must be recorded on the appropriate eCRF page.

For this trial, it is not allowed to have received an experimental agent within 60 days prior to screening. In addition, use of previous gene therapy is not allowed.

5.6.2 Concomitant Medication/Therapy

Concomitant medication/therapy is defined as any medication/therapy being continued by the subject at the date of screening, and any new medication/therapy received during the trial. Concomitant medication/therapy must be recorded on the appropriate eCRF page.

The following treatments will not be allowed during trial participation:

- Continuous routine factor IX prophylaxis post-dose if a subject's endogenous factor IX activity result is above 5%
- Treatment in another interventional clinical trial involving drugs or devices within one year from IMP administration in this trial
- Another gene therapy treatment
- Chronic administration of steroids (oral and/or inhaled)

Apart from the above listed treatments, no protocol restrictions will apply with respect to concomitant treatment.

Version:	4.0	(Amendment 3.0)
----------	-----	-----------------

At baseline, subjects will be administered a challenge dose of short-acting factor IX (40 IU/kg) for the factor IX recovery assessment. This challenge dose should provide subjects sufficient factor IX coverage for the initial two to three days post treatment. Three days after IMP administration, the subjects should visit the clinic for endogenous factor IX activity assessment. If the factor IX activity result is \geq 5%, further factor IX prophylaxis will not be given. If the factor IX activity result is <5%, another dose of short-acting factor IX will be administered to the subject and endogenous factor IX activity assessment will be performed again at the Week 1 routine visit.

Additional on-demand factor IX may be given after treatment with AMT-061, if considered necessary. If the endogenous factor IX activity result is \geq 5%, management will be based on the Investigator's clinical judgement and subject preference. Re-initiation of factor IX continuous routine prophylaxis may be considered if the endogenous factor IX activity is between 2 and 5% in at least two consecutive laboratory measurements, based on the Investigator's clinical judgment and subject preference. If the endogenous factor IX activity is below 2% in at least two consecutive central lab measurements, continuous routine factor IX prophylaxis may be restarted.

Factor IX infusions are not recommended for subjects with factor IX activity in the non-hemophilic (\geq 40% of normal) range especially in subjects with a confirmed COVID-19 infection, as increased thrombogenic risk is a known complication of COVID-19. Subjects with factor IX activity in the non-hemophilic range post-treatment with AMT-061 and infected with COVID-19 may potentially be at the same risk of thrombosis as subjects without hemophilia; antithrombotic therapy for these subjects should be considered under the same guidelines recommended for those without hemophilia.

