1.5.9 Risk of Breakthrough Bleeding

The scope of the liver-directed AAV gene therapy approach is to establish a stable and durable expression of factor IX and to convert to mild or completely ameliorate the severe hemophilia phenotype. Previous clinical trials with similar AAV vectors and the wild-type gene cassette have shown that stable and years long factor IX expression can be achieved (Nathwani et al., 2014). Nonetheless, there is a risk that breakthrough bleeding may occur, particularly if demanding physical activity is undertaken. This risk will be managed by the use of factor IX replacement as needed throughout the trial. Every effort will be made to avoid routine use of prophylactic factor IX replacement therapy during the trial.

In a previous trial with AMT-060, therapeutic levels of factor IX protein and resultant factor IX activity levels were seen as early as one week after treatment.

At baseline, subjects will be administered a challenge dose of short-acting factor IX (40 IU/kg) for the factor IX recovery assessment. This challenge dose should provide subjects sufficient factor IX coverage for the initial two to three days post treatment. Three days after IMP administration, the subjects should visit the clinic for endogenous factor IX activity assessment (by local laboratory). If the factor IX activity result is \geq 5%, further factor IX prophylaxis will not

be given. If the factor IX activity result is <5%, another dose of short-acting factor IX will be administered to the subject and endogenous factor IX activity assessment will be performed again at the week 1 routine visit.

Additional on-demand factor IX may be given after treatment with AMT-061, if considered necessary. Furthermore, subjects are monitored closely for five years after administration of IMP and the need for renewed prophylactic therapy will be clinically assessed by the treating physician according to the local standard of care for hemophilia subjects.

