6.1.2 IMP Administration

The day of IMP administration should be planned to take place as an overnight stay at the clinic and should take place within a maximum of six weeks after the Screening visit (unless sponsor approved a prolonged screening period as described in Section 6.1.1).

The baseline visit should also be planned as such that the baseline blood sample for factor IX activity and factor IX protein concentration assessment will be drawn at the point in time where factor IX activity and factor IX protein concentration is expected to be closest to trough levels (i.e., the baseline visit should be scheduled on days when routine factor IX prophylaxis is due to be administered). In case of on-demand factor IX replacement therapy use in proximity to the scheduled visit, the exogenous factor IX is to be washed out and the visit is to be rescheduled to the extent the visit window allows. The wash out period will be minimal 10 days for short-acting factor IX or more for long-acting factor IX (depending on half-life).

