For the Week 6 and 52-Week data-cut analyses, the contamination rule, as stated above, was 10 (discrete) days. Specifically - Factor IX activity levels during the period of use or within 10 days after the end of use of exogenous factor IX replacement therapy were not included in these analyses; the last (calendar) day of use and the subsequent nine (calendar) days are considered to be contaminated. Beginning with the 2.5-year (data cut) analysis, the contamination rule is hereby refined as follows. Factor IX assessments post-AMT-061 that are within 5 half-lives of exogenous factor IX use are considered contaminated and will be excluded from the analysis. Going forward, this 5-half-life contamination rule replaces the 10-day contamination rule. Both the date and time of the exogenous factor IX infusion start and the blood sampling for factor IX activity assessment will be taken into account to determine whether there was contamination. If the factor IX activity assessment was performed prior to the infusion start time, then the assessment is not considered to be contaminated by that infusion. See further detail in the [Data Handling Rules Appendix](#) in this document [under the category of “Contamination due to exogenous factor IX (infusion) use”].

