6.7.2 Secondary Efficacy Endpoints

FIX activity over 52 weeks (and 2.5 years) (post IMP administration), annualized FIX consumption, Prophylaxis FIX replacement therapy use over 52 weeks (and 2.5 years), and on-demand FIX replacement therapy use over 52 weeks (and 2.5 years) will be presented using descriptive statistics across subjects for each visit and across time for each subject.

Bleeding episodes and annualized bleeding rates in the post-prophylaxis period and type (spontaneous bleeds, joint bleeds, and traumatic bleeds) will also be presented using descriptive statistics. All events that are emergent during the period will be counted.

The end of continuous prophylaxis requires 3 events: (1) study drug was administered, (2) uncontaminated factor IX activity (post-study drug) has since been observed to be $\geq 5\%$, and (3) the subject has not used exogenous factor IX for some contiguous time period of at least 15 days after study drug administration. The tenth day of the first 15-day contiguous period where these criteria are met is then taken as the end of prophylaxis. The Post-Continuous-Prophylaxis period begins on the day after the end of continuous prophylaxis. If the field for whether the bleed was treated is missing, then (for conservativeness) it will be assumed that the bleed was treated with factor IX. If the assessment field for newness of the bleed is missing, then (for conservativeness) it will be assumed that the bleed is new. If the assessment field for trueness of the bleed is missing, then (for conservativeness) it will be assumed that the bleed is true. A supplemental analysis will count only bleeds that were treated with exogenous factor IX. A supplemental analysis will count only bleeds that are assessed by the investigator to be new and true bleeds (per entry on the CRF).

[figure not shown]
In the analysis (from the 2.5-year data cut henceforth), any person-time during the post-treatment period within 5 half-lives subsequent to exogenous factor IX use will not be counted in the time at risk of (having) a bleeding event. Both the date and time of the exogenous factor IX injection start will be taken into account to identify time periods to be excluded. Nevertheless, any bleeds occurring during the post-prophylaxis period should still be counted as events, even if they

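### The Day 3 factor IX value that stops prophylaxis at 5% is called endogenous but is total activity, drawn inside the washout of the Day 0 challenge dose

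*Protocol*

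**What the plan says.** The rule stands in the Protocol synopsis and in sections 1.5.9 and 5.6.2. Each subject receives 40 IU/kg of short-acting factor IX at baseline for the recovery assessment, and section 5.6.2 adds: "This challenge dose should provide subjects sufficient factor IX coverage for the initial two to three days post treatment". Then comes the decision sample: "Three days after IMP administration, the subjects should visit the clinic for endogenous factor IX activity assessment". Section 1.5.9 names the laboratory: "the subjects should visit the clinic for endogenous factor IX activity assessment (by local laboratory"). Protocol Table 2 schedules a local one-stage aPTT sample on Day 3 with a window of ±1 day and no central sample.

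At 5% or more, no further prophylaxis is given. Below 5%, sections 1.5.9 and 5.6.2 give another short-acting dose and repeat the test at Week 1. Section 5.6.2 also lists as not allowed: "Continuous routine factor IX prophylaxis post-dose if a subject's endogenous factor IX activity result is above 5" per cent.

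Elsewhere the documents say when a level is free of infused product:

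- Protocol 6.1.2, on planning the baseline sample: "The wash out period will be minimal 10 days for short-acting factor IX or more for long-acting factor IX (depending on half-life").
- Protocol 9.9.1 requires 10 days before a level counts as unaffected.
- SAP 6.7.1, from the 2.5-year analysis: "Factor IX assessments post-AMT-061 that are within 5 half-lives of exogenous factor IX use are considered contaminated".
- SAP 6.7.2, as one condition for the end of continuous prophylaxis: "uncontaminated factor IX activity (post-study drug) has since been observed to be" at least 5%.

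**The concern.** The same text that expects the challenge dose to protect the subject for two to three days then reads a sample at two to four days as the subject's own production. A one-stage clotting assay measures infused factor IX too; Protocol 6.2.3.7 uses that assay type to measure recovery of the challenge.

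The error has one direction. Infused product can only raise the reading, so it can withhold the preventive dose but never add one. A subject with no transgene expression could pass 5% on infused product and go uncovered until the next weekly test. This is the first trial of AMT-061 in humans, so early expression should not be presumed. The early expression described in Protocol 9.2 comes from the earlier product, and a Day 3 total value cannot show whether it has occurred.

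Two further sources push the reading up. Inclusion criterion 3b admits an own level of 1–2%. For subjects on routine prophylaxis the baseline sample is taken at trough and not after washout ("the baseline visit should be scheduled on days when routine factor IX prophylaxis is due to be administered"), so earlier product may remain. The size of that second source cannot be derived from the documents.

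**Working it through.** The plan gives no residual figure, so there is none to reproduce.

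**Step 1: calendar, from the documents alone.** Under the 10-day rule as SAP 6.7.1 spells it out, the day of use and the next nine days are contaminated, that is, Day 0 to Day 9. The Day 3 window is Day 2 to Day 4, wholly inside. Under the 5-half-life rule a 72 h sample is clean only if the half-life is at most 72/5 = 14.4 h. The limits are 48/5 = 9.6 h at Day 2 and 96/5 = 19.2 h at Day 4.

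**Step 2: residual, under assumptions.** Recovery R of 0.6–1.0% per IU/kg and half-life T of 18–24 h are assumed; neither is in the documents. The dose of 40 IU/kg is from section 5.6.2.

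- Residual (%) = 40 × R × 2^(−t/T)
- Hours until a non-expressing subject with own level o (%) reads below 5% = T × log2(40R / (5 − o))

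| | R 0.6, T 18 h | R 0.8, T 21 h | R 1.0, T 24 h |
|---|---|---|---|
| Initial rise, 40R (%) | 24 | 32 | 40 |
| Residual at 48 h (%) | 3.78 | 6.56 | 10.00 |
| Residual at 72 h (%) | 1.50 | 2.97 | 5.00 |
| Residual at 96 h (%) | 0.60 | 1.35 | 2.50 |
| Hours to below 5%, own level 0 | 40.7 | 56.2 | 72.0 |
| Hours to below 5%, own level 1% | 46.5 | 63.0 | 79.7 |
| Hours to below 5%, own level 2% | 54.0 | 71.7 | 89.7 |

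At 48 h, mid-range kinetics already exceed 5% with no own level. With an own level of 2%, even the low corner does (3.78 + 2 = 5.78). At 72 h with no own level, only the extreme corner reaches 5.00. Mid-range kinetics plus 2% give 2.97 + 2 = 4.97, so the dose is still given. With R = 1.0, 5% is reached at 72 h for a half-life of 21.7 h or more (own level 1%) or 19.3 h or more (own level 2%). At 96 h the highest reading is 2.50 + 2 = 4.50, so the late side of the window gives no false stop.

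With recovery taken as 0.7–1.2 instead, the residual is 4.4–12.0% at 48 h and 1.8–6.0% at 72 h. The pattern is the same, somewhat higher.

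**Step 3: duration of the gap.** The challenge falls below 1% at T × log2(40R). Among cases where the 48 h residual alone is at least 5%, the latest crossing is 24 × log2(40) = 127.7 h (Day 5.3). The earliest is at T = 18 h, where 40R must be at least 5 × 2^(48/18) = 31.7; this gives 89.8 h (Day 3.7). The gap to a nominal Day 7 visit is therefore about 1.7 to 3.3 days, for a subject with no own level and no expression.

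**Step 4: when a clean value exists.** Five half-lives are 90–120 h (Day 3.75–5), so Week 1 (Day 7 ±2, that is Day 5–9) is clean if no Day 3 dose was given. After a dose on Day 3 the clean time is Day 6.75–8, and after a dose on Day 4 it is Day 7.75–9, so Week 1 is not reliably clean. Week 2 (Day 12–16) is.

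**The case against.** The strongest reply has four parts.

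- **The contamination rules serve other purposes.** They govern descriptive statistics and baseline sampling, while Protocol 6.2.2.3 keeps local results for monitoring. For a same-day decision total activity is relevant, since a subject who reads 5% has 5% at that moment. This stands as far as current cover goes. It does not support calling the value endogenous or letting it end prophylaxis, and SAP 6.7.2 ties the same threshold to an uncontaminated value.
- **Safeguards limit the harm.** Local factor IX is tested weekly in Weeks 1–12, on-demand product stays available, and section 5.6.2 leaves management at 5% or more to the investigator and the subject. This stands.
- **The size rests on outside kinetics.** It does, and the 72 h result is sensitive to them. Step 1 is not. A false stop at 72 h mostly needs an own level of 1–2%, and such a subject does not fall below that level afterwards.
- **The decision has probably passed.** The log for Amendment 2 (February 2021) describes all subjects as approaching Month 30, and SAP 6.1 refers to the 12-month analysis in the past tense. This stands and sets the severity. For subjects already dosed, Protocol 9.9.1 already plans a flag for contaminated values in the listings.

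A reader might infer that the primary result is biased. The documents do not support this: Week 6 is Day 42, contaminated values are excluded from the summaries, and SAP 6.7.1 moves to a later visit if product was used within 10 days. Nor do they support reading the rule as barring all factor IX. The item on treatments not allowed covers only continuous routine prophylaxis.

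**Conclusion.** Wrong as written, low severity. That the Day 3 value lies inside the washout follows from the documents alone. That it can reach 5% without expression depends on the assumed recovery and half-life: likely at a Day 2 visit, and at 72 h only with an own level of about 1–2% or kinetics at the extreme of the range. The likely loss is one preventive dose and a few days of reduced cover. It would go too far to say that subjects at the scheduled 72 h visit would generally be stopped in error, since with mid-range kinetics the dose is still given. Nothing in the documents shows that any treated subject was harmed. The change matters only if subjects are added, which Protocol 9.12 and SAP 3.3 allow.

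**What to change.** In the synopsis, sections 1.5.9 and 5.6.2, and the Day 3 column of Tables 1 and 2, for any added subjects:

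1. Call the Day 3 value total activity. Change its window from ±1 day to 0/+1 day, with the sample at least 72 h after the challenge.
2. Treat a Day 3 value of 5% or more as evidence of current cover only. Apply the 5% stop, and the item on treatments not allowed, first to a local value at least 5 half-lives after the last infusion. Use visits already scheduled: Week 1 if no Day 3 dose was given, otherwise Week 2. Leave cover in between to the investigator. For a subject coming from long-acting prophylaxis, count that product's half-lives from its own last dose as well.

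If the 10-day rule of Protocol 9.9.1 is preferred, the first clean visit is Week 2 in every case.

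Cost: text changes, a tighter visit window, possibly an extra short-acting dose, and no new visit or assay. An extra dose on Day 3 or 4 could delay by about three to four days the 15-day period without exogenous factor IX that SAP 6.7.2 uses to date the end of prophylaxis.
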